6.1. Primary Study Endpoints

Co-Primary Endpoints:

- 1a. Correct classification of subjects with normal sinus rhythm (HR 50-150) on simultaneous 12-lead ECG as “Sinus Rhythm” or “High Heart rate” on a readable and classifiable ECG app strip. [Specificity]

1b. Correct classification of subjects with AF (HR 50-150) on simultaneous 12-lead ECG as “AF” or AF (high heart rate) on a readable and classifiable ECG app strip. [Sensitivity]

6.2. Secondary Endpoints

2a. Correct classification of subjects with normal sinus rhythm (HR 50-99, sinus rhythm (SR) on simultaneous 12-lead ECG) as “Sinus Rhythm” on a readable and classifiable ECG app strip

2b. Correct classification of subjects with AF (HR 50-99, AF on simultaneous 12-lead ECG) as “AF” on a readable and classifiable ECG app strip

[figure not shown]
2c. Correct classification of subjects with sinus tachycardia (HR 100-150, SR on simultaneous 12-lead ECG) as “High Heart Rate” on a readable and classifiable ECG app strip

[figure not shown]
2d. Correct classification of subjects with AF with high heart rate (HR 100-150, AF on simultaneous 12-lead ECG) as “AF (high heart rate)” on a readable and classifiable ECG app strip

2e. Equivalence of the ECG app waveform to Lead I from a 12-lead ECG as measured by acceptable morphology of PQRST complexes

2f. Equivalence of the ECG app waveform to Lead I from a 12-lead ECG as measured by R-Wave amplitude agreement

6.3. Study Hypotheses

7. Statistical Considerations

7.1. Sample Size

[REDACTED] The sample sizes to achieve 80% power with a one-sided type I error of 0.025 using an exact binomial test are [REDACTED] with no known diagnosis of AF and [REDACTED] with a known diagnosis of AF.

Table 7.1 below presents the expected percent correct associated with the four secondary endpoints 2a, 2b, 2c, and 2d and are summarized below along with the proposed performance goals.

Table 7.1: Sample size determination for four secondary endpoints

[REDACTED] To account for obtaining readable/classifiable waveforms and to ensure enough data is collected from the exercise stage, 168 subjects with no known diagnosis of AF and 400 subjects with a known diagnosis of AF will be enrolled.

[REDACTED] To account for obtaining readable waveforms and to assess waveform equivalence across a

range of heart rates and rhythms, approximately 100 subjects (50 SR; 50 AF) will be randomly selected according to the sampling scheme presented in Section 7.2.

7.2. Randomization and Blinding

Subjects in this study will not be randomized to any treatment regimens.

Approximately 100 subjects (50 SR; 50 AF) will be randomly selected to assess waveform equivalence of the ECG app to Lead 1 from a 12-Lead ECG. Subjects will be randomly selected using a systematic sampling approach. A number between 1 and 6 will be randomly selected for the AF cohort and then every 6th consecutively enrolled AF subject will be selected at random within each site. Likewise, a number between 1 and 5 will be randomly selected for the SR cohort and then every 5th consecutively enrolled SR subject will be selected at random within each site.

US board-certified cardiologists will be blinded to the subjects' past medical history, stage (resting or exercise) and ECG app classifications during the assessment and adjudication of ECG data.

Cardiac technicians will be blinded to the subjects' past medical history, ECG app classifications, stage (resting or exercise) and origin (ECG app or 12-lead ECG) of the waveform being reviewed during the assessment and adjudication of ECG data.

Adjudicators will be instructed to review ECGs independently and separately of each other and not to confer about diagnoses.

7.3. Significance Level

The primary hypothesis, the four secondary endpoint hypothesis tests of percent correct, and the two secondary endpoint hypotheses of waveform assessment will use a one-sided significance level of 0.025.

7.4. Missing Data

Rigorous efforts will be made to ensure all subjects are compliant with the protocol. However, some subjects may drop out prematurely or some planned measurements may not be analyzable due to missing data or uninterpretable results from either the ECG adjudication process or the ECG app test device. The data analyses will be conducted on all analyzable data.

7.5. Subgroup Analyses

In accordance with the FDA Guidance⁸ on the reporting of age-, race-, and ethnicity-specific data, the primary endpoints will be reported by the following subgroups (data permitting). Some subgroups may be combined depending on data availability.

- Age group (<55; ≥55 to <65; ≥65 years)

- Sex (Male; Female)
- Race (White; Black or African American; Asian; American Indian or Alaska Native; Native Hawaiian or other Pacific Islander)
- Ethnicity (Hispanic or Latino; Not Hispanic or Latino)
- Watch series/material types (Series 4, Series 5: Aluminum, ceramic, titanium, stainless steel)

7.6. Interim Analyses

There are no interim analyses planned in this study.

8. Analysis Sets

The following analysis sets are defined for this study.

Full Analysis Set (FAS): All subjects who sign informed consent and are enrolled into the study. This analysis set will be used to summarize subject 12-Lead, and ECG app device accountability in addition to demographic and baseline characteristics and safety data. The data for this analysis set will be presented overall and separately for the enrollment cohorts.

Classifiable Analysis Set (CAS): All subjects who have readable paired ECG app and 12-Lead ECG adjudicated results. This analysis set will be used for analyzing the co-primary endpoints (1a, 1b), the four secondary endpoints (2a, 2b, 2c, and 2d) and the additional analyses.

Waveform Assessment Analysis Set (WAAS): Randomly selected subjects with readable paired strips from the ECG app and Lead 1 of the 12-Lead ECG. If 6 consecutive beats for analysis cannot be found in these strips, they will be excluded from further analysis. This analysis set will be used for assessing the clinical waveform accuracy associated with secondary endpoints 2e and 2f.

9. Analysis Approach

9.1. Dataset Generation

A single sensor dataset to generate ECG app waveforms and classifications will be used for this study to which the test device algorithm will be applied in a post-hoc fashion.

9.2. Subject Accountability

A summary of the number of enrolled subjects, eligible subjects, withdrawn subjects, and completers will be presented by cohort assigned at baseline (SR or AF), overall, and by investigational site. Reasons for withdrawal will be summarized according to the following categories:

- Adverse Event

- Death
- Protocol Deviation
- Withdrawal of Consent
- Investigator Discretion
- Termination of the Study
- Device malfunction
- Lost to Follow-up
- Other

9.3. ECG App and 12-Lead ECG Measurement Accountability

A summary table will be reported which presents the accountability of ECG app and 12-Lead ECG test measurement results overall and by enrollment cohort.

9.4. Demographic Characteristics

Descriptive statistics (e.g., N, Mean, Std. Dev., Min, Max) for continuous data types and frequencies for categorical data types will be displayed for the demographic characteristics by cohort assigned at baseline (SR or AF), overall, and by investigational site. The demographic characteristics and data types are listed below:

Table 9.1: Demographic Characteristics

Characteristic	Data Type
Age at Enrollment (years)	Continuous
Age Group at Enrollment	Categorical
Sex	Categorical
Ethnicity	Categorical
Race	Categorical

The following age group categories will be used: <55, ≥55 to <65, and ≥65 years. Subjects may choose more than one Race category.

9.5. Baseline Characteristics

The following baseline characteristics will be summarized using descriptive statistics by enrollment cohort assigned at baseline (SR or AF) and overall.

9.5.1. History of Heart Rhythm Abnormalities

Heart rhythm abnormalities will be summarized with frequencies and percentages according to the following categories:

- None
- AF (permanent)
- AF (persistent)
- AF (paroxysmal)
- AF (other)

- Atrial flutter
- Ventricular Tachycardia
- Atrial Tachycardia
- 1st degree AV block
- 2nd degree AV block (Type I)
- 2nd degree AV block (Type II)
- 2nd degree AV block (other)
- Left Branch Bundle Blockage (LBBB)
- Right Branch Bundle Blockage (RBBB)
- Other

9.5.2. Baseline Electrocardiogram Results

The baseline ECG results at screening will be summarized descriptively as follows:

Table 9.2: ECG Results at Screening

Characteristic	Data Type
Ventricular rate (bpm)	Continuous
PR interval (msec)	Continuous
QRS duration (msec)	Continuous
QT interval (msec)	Continuous
RR interval (msec)	Continuous
QTc (msec)	Continuous
QTcB (msec)	Continuous
QTcF (msec)	Continuous
Rhythm	Categorical
Results interpretation (normal/abnormal)	Categorical

Abnormal ECG findings will be further summarized by clinical significance (yes/no).

9.5.3. Lifestyle Characteristics

Responses to the lifestyle questions will be summarized descriptively as follows:

Table 9.3: Lifestyle Characteristics

Characteristic	Data Type
Tobacco/nicotine use	Categorical
Alcohol use	Categorical
Recreational drug use	Categorical
Caffeine use	Categorical
Exercise	Categorical

9.5.4. Physical Exam Results

Results of the physical examination will be summarized as normal/abnormal for the following anatomical categories:

- General appearance
- Head, eyes, ears, and nose
- Chest
- Heart
- Abdomen
- Musculoskeletal
- Neurologic
- Dermatologic

Tremors will also be summarized as present/absent along with descriptive statistics of tremor severity on a scale of 0-10 for those with tremors present. The number of subjects who have tattoos on sensor locations will also be summarized. Pregnancy test results will also be summarized.

9.5.5. Vital Signs

Results of the vital signs assessments will be summarized descriptively for the following parameters:

- Systolic blood pressure (mmHg)
- Diastolic blood pressure (mmHg)
- Heart rate (bpm)
- Body temperature (°C)

9.5.6. Medical History

Medical and allergy history information will be coded using MedDRA v22.1 and summarized by preferred term.

9.5.7. Body and Device Wear Measurements

Body and device wear measurement results at baseline will be summarized descriptively as follows:

Table 9.4: Body and Device Wear Measurements

Characteristic	Data Type
Height (cm)	Continuous
Weight (kg)	Continuous
BMI (kg/ m ²)	Continuous
Dominant hand	Categorical
Preferred wrist to wear a band on	Categorical
Device wearing wrist circumference (mm)	Continuous
Device wearing wrist skinfold thickness (mm)	Continuous
Device wearing wrist hairiness	Categorical
Wrist device size	Categorical
Band size	Categorical
Device wearing wrist	Categorical

Characteristic	Data Type
Wrist device location	Categorical
Wrist device orientation	Categorical
Wrist device interaction	Categorical

9.6. Primary Endpoint Analyses

The following truth table will be generated to cross-classify data collected from enrolled subjects according to the ECG app device and adjudicated ECG data from the 12-lead ECG for the primary endpoint analyses as presented below. The rhythm classification and the heart rate will be adjudicated separately. The final adjudicated rhythm classification result will be used if there is a rhythm classification discrepancy (including the specify type of Other Abnormal Rhythm) between the first two cardiologists. The final adjudicated heart rate result will be used if there is a heart rate discrepancy between the first two cardiologists.

Table 9.5: Cross-classification truth table for primary endpoint analyses

Algorithm Classification	Reference Strip Final Adjudicated Result (via 3 US Board Certified Cardiologists)			
	SR ($50 \leq HR \leq 150$)	AF ($50 \leq HR \leq 150$)	Other (SVT or Other with HR 50-150; HR<50; HR>150)	Uninterpretable
SR (SR (50-100) + High HR no AF (101-150))	n11	n12	n13	n14
AF ($50 \leq HR \leq 150$)	n21	n22	n23	n24
Inconclusive (including HR< 50; HR>150)	n31	n32	n33	n34
Poor Recording	n41	n42	n43	n44

Note: Bold indicates data values used for the primary endpoint analyses.

The following primary endpoint hypothesis will be tested using a one-sided type I error of 0.025:

██

██

Using the cross-classified data from Table 9.5, the sensitivity and specificity for the primary endpoint hypothesis will be estimated as follows:

$$\text{Sensitivity estimate} = n_{22}/(n_{12} + n_{22})$$

$$\text{Specificity estimate} = n_{11}/(n_{11} + n_{21})$$

Each subject may contribute up to 2 paired ECG app and Adjudicated 12-Lead ECG results for analysis; one at rest (first trial run) and the other after exercise (first trial run).

Because data will be collected from the same subjects at rest and after exercise, a bootstrap approach will be implemented to obtain two-sided 95% confidence intervals for the sensitivity and specificity to account for potential within-subject correlation. Subjects with at least one adjudicated result of AF (for sensitivity), SR (for specificity) and with a classifiable algorithm result (i.e., SR or AF) will be selected at random with replacement and the 2.5th and 97.5th percentiles of the distribution of bootstrap estimates will represent the two-sided 95% confidence bounds. If the lower confidence bounds for both sensitivity and specificity exceed the pre-established performance goal associated with these performance metrics, the null hypothesis will be rejected in favor of the alternative hypothesis. Sensitivity and specificity estimates will also be presented separately for at rest and after exercise measurements along with their corresponding Fisher’s Exact 95% confidence intervals.

As an additional analysis associated with the primary endpoint, the sensitivity and specificity will also be estimated and reported along with their corresponding bootstrap two-sided 95% confidence intervals by including the Inconclusive algorithm classification category in the calculation. More specifically, the sensitivity and specificity for the additional analysis will be estimated as follows:

$$\text{Sensitivity estimate (additional analysis)} = n_{22}/(n_{12} + n_{22}+n_{32})$$

$$\text{Specificity estimate (additional analysis)} = n_{11}/(n_{11} + n_{21}+n_{31})$$

9.7. Secondary Endpoint Analyses

The following truth table will be generated to cross-classify data collected from enrolled subjects according to the ECG app device and adjudicated ECG data from the 12-lead ECG for secondary endpoint analyses as presented below:

Table 9.6: Cross-classification truth table for secondary endpoint analyses

ECG app Device	Ground Truth via Adjudicated 12-lead ECG									
	HR	<50	50-99	50-99	100-150	100-150	>150	50-150		

Output	Rhythm	Any	SR	AF	SR	AF	Any	SVT or Other	Uninterpretable	Total
Low HR (<50)		n11	n12	n13	n14	n15	n16	n17	n18	N1D
SR (50-99)		n21	n22	n23	n24	n25	n26	n27	n28	N2D
AF (50-99)		n31	n32	n33	n34	n35	n36	n37	n38	N3D
High HR (100-150) with no AF		n41	n42	n43	n44	n45	n46	n47	n48	N4D
AF (100-150)		n51	n52	n53	n54	n55	n56	n57	n58	N5D
HR >150		n61	n62	n63	n64	n65	n66	n67	n68	N6D
Inconclusive		n71	n72	n73	n74	n75	n76	n77	n78	N7D
Poor Recording		n81	n82	n83	n84	n85	n86	n87	n88	N8D
Total		N1	N2	N3	N4	N5	N6	N7	N8	N

Note: Bold indicates data values used for the secondary endpoint analyses.

The following four secondary endpoint hypotheses will be tested:

[REDACTED]

[REDACTED]

[REDACTED]

[REDACTED]

[REDACTED]

[REDACTED]

[REDACTED]

[REDACTED]

[REDACTED]

[REDACTED]

[REDACTED]

[REDACTED]

[REDACTED]

Using the cross-classified data from Table 9.6, the percent correct for each of the four secondary endpoint hypotheses will be estimated as follows:

Hypothesis 2a: Percent Correct = $n_{22}/(n_{22}+n_{32}+n_{42}+n_{52})$

Hypothesis 2b: Percent Correct = $n_{33}/(n_{23}+n_{33}+n_{43}+n_{53})$

Hypothesis 2c: Percent Correct = $n_{44}/(n_{24}+n_{34}+n_{44}+n_{54})$

Hypothesis 2d: Percent Correct = $n_{55}/(n_{25}+n_{35}+n_{45}+n_{55})$

Each subject may contribute up to 2 paired ECG app and Adjudicated 12-Lead ECG results for analysis; one will be at rest (first trial) and the other after exercise (first trial).

Because data will be collected from the same subjects at rest and after exercise, a bootstrap approach will be implemented to obtain two-sided 95% confidence intervals for the percent correct associated with each of the four secondary endpoint hypotheses to account for potential within-subject correlation. Subjects with at least one adjudicated result of SR (HR 50-99) [hypothesis 2a], AF (HR 50-99) [hypothesis 2b], SR (HR 100-150) [hypothesis 2c], AF (HR 100-150) [hypothesis 2d] and with a classifiable algorithm result will be selected at random with replacement and the 2.5th and 97.5th percentiles of the distribution of bootstrap estimates will represent the two-sided 95% confidence bounds. If the lower confidence bound of the percent correct equals or exceeds the pre-established performance goal associated with the associated secondary endpoint hypotheses, the null hypotheses will be rejected in favor of the alternative hypotheses.

Additional secondary endpoint analyses will be performed similarly by including the HR<50, HR>150, and Inconclusive algorithm results in the computations of percent correct.

Two hypotheses associated with secondary objective to demonstrate that the ECG app produces a waveform that provides clinically equivalent information to Lead 1 of the 12-Lead ECG will be tested.

[REDACTED]

The majority result from the pass/fail readings of the 3 independent, certified cardiac technicians will be used for analysis. The hypothesis for this objective is stated as follows:

[REDACTED]

[REDACTED]

The second hypothesis will be based on the results of the quantitative analysis of the R-wave amplitudes as measured by each of 3 independent, certified cardiac technicians on the paired ECG app and Lead 1 from the 12-Lead ECG reference strips. The majority result

from the three technicians (i.e., if at least two technicians measured the difference in amplitudes between the ECG app and reference strips to be ≤ 2 mm then the paired strips for a given subject were deemed ≤ 2 mm) was used [REDACTED]

[REDACTED]

[REDACTED]

[REDACTED]

For each subject, the QRS complex from the 12-lead ECG with the largest R amplitude (out of the two QRS complexes with R-wave amplitude measurements) will be used for purposes of determining the majority result.

Due to the multiple observations per subject while at rest and during exercise, a bootstrap approach will be used to construct two-sided 95% confidence intervals for the Morphology Pass Rating Proportion and the R-Wave Amplitude Agreement Proportion. If the lower 2.5th percentile of the bootstrap distribution for the Morphology Pass Rating Proportion [REDACTED], the null hypothesis $H_{0,2e}$ will be rejected. [REDACTED] to the evaluation of the R-Wave Amplitude Agreement Proportion.

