Because data will be collected from the same subjects at rest and after exercise, a bootstrap approach will be implemented to obtain two-sided 95% confidence intervals for the sensitivity and specificity to account for potential within-subject correlation. Subjects with at least one adjudicated result of AF (for sensitivity), SR (for specificity) and with a classifiable algorithm result (i.e., SR or AF) will be selected at random with replacement and the 2.5th and 97.5th percentiles of the distribution of bootstrap estimates will represent the two-sided 95% confidence bounds. If the lower confidence bounds for both sensitivity and specificity exceeds the pre-established performance goal associated with these performance metrics, the null hypothesis will be rejected in favor of the alternative hypothesis.

As an additional analysis associated with the primary endpoint, the sensitivity and specificity will also be estimated and reported along with their corresponding bootstrap two-sided 95% confidence intervals by including the Inconclusive algorithm classification category in the calculation. More specifically, the sensitivity and specificity for the additional analysis will be estimated as follows:

$$\text{Sensitivity estimate (additional analysis)} = n_{22}/(n_{12} + n_{22} + n_{32})$$

$$\text{Specificity estimate (additional analysis)} = n_{11}/(n_{11} + n_{21} + n_{31})$$

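### The 2a–2d success rule counts a lower bound that merely equals the goal, unlike the co-primary rule; a small, no-cost wording inconsistency whose effect is usually slight

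*SAP*

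**What the plan says.** The decision rule for the four percent-correct endpoints (SAP 9.7, repeated in Protocol 6.2.2) rejects the null "If the lower confidence bound of the percent correct equals or exceeds the pre-established performance goal". The co-primary rule is strict: SAP 9.6 has "If the lower confidence bounds for both sensitivity and specificity exceed the pre-established performance goal" and Protocol 6.2.1 has "If the lower confidence bounds for both sensitivity and specificity exceeds the pre-established performance goal".

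Both rules use the same interval, a percentile bootstrap in which subjects "will be selected at random with replacement and the 2.5th and 97.5th percentiles of the distribution of bootstrap estimates" and those percentiles serve as the bounds. Both are held to the same error rate: under SAP 7.3 the primary test and all six secondary tests "will use a one-sided significance level of 0.025", and Protocol 6.4 agrees.

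The hypotheses, the performance goals and the sample sizes required for power are redacted. So is the comparison with the goal for waveform endpoints 2e and 2f. The decision sentences for 1a/1b and 2a–2d are intact.

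**The concern.** A lower confidence bound that sits on the goal leaves the goal inside the interval, so the data have not excluded it. A rule that accepts equality can only turn failures into successes, never the reverse. If equality can occur, the secondary tests carry a higher false-success rate than the strict rule used for the co-primary endpoints, under the same nominal 0.025.

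Equality can occur because percent correct is a ratio of counts. If each subject in a category gives one recording, the denominator n is the same in every resample, and the bootstrap percentiles fall on multiples of 1/n. When goal × n is a whole number, the bound can land exactly on the goal. This is most plausible for 2a, fed mainly by rest recordings, and 2c, fed mainly by exercise recordings. It is less so for 2b and 2d, where an AF subject may have both recordings in one heart-rate band.

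At stake is whether a borderline secondary claim counts as met.

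**Working it through.** **The plan's own figures.** SAP 7.1 states 80% power by exact binomial test at one-sided 0.025, but the required n, the goals and the expected rates are redacted, so that calculation cannot be reproduced. What can be confirmed is that the 2.5th percentile, as the lower end of a two-sided 95% interval, corresponds to a nominal one-sided 0.025.

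**Assumed inputs.** Goal g from 0.80 to 0.95; n from 60 to 400 recordings in a category. For scale, the enrolment targets in SAP 7.1 are 168 subjects without and 400 with an AF diagnosis. SAP section 11 says enrolment stopped short of target and does not give the number reached.

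**Step 1: one recording per subject.** With x correct out of n, the ideal bootstrap distribution of the count is Binomial(n, x/n). The lower bound is L(x)/n, where L(x) is its 2.5% quantile (the smallest count with cumulative probability of at least 0.025). With the true rate at the goal:

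- strict rate = sum of P(X = x | n, g) over x with L(x) > g·n
- rate as written = the same sum over x with L(x) ≥ g·n

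Example, g = 0.90 and n = 100, so g·n = 90:

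- x = 95: Binomial(100, 0.95) puts 1.15% at or below 89 and 2.82% at or below 90, so L = 90, an exact tie.
- x = 96: Binomial(100, 0.96) puts 1.90% at or below 91 and 4.75% at or below 92, so L = 92, above the goal.

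The rule as written succeeds from x = 95, and P(X ≥ 95 | 0.90) = 5.8%. The strict rule succeeds from x = 96, and P(X ≥ 96 | 0.90) = 2.4%. The ratio is 2.4.

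| Goal | n | Strict | As written | Ratio |
|---|---|---|---|---|
| 0.80 | 200 | 2.8% | 4.3% | 1.5 |
| 0.90 | 100 | 2.4% | 5.8% | 2.4 |
| 0.90 | 200 | 3.2% | 5.7% | 1.8 |
| 0.90 | 400 | 2.35% | 3.6% | 1.5 |
| 0.95 | 100 | 3.7% | 11.8% | 3.2 |
| 0.95 | 200 | 2.6% | 6.2% | 2.4 |
| 0.90 | 168 | 4.5% | 4.5% | 1.0 |

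In the last row 0.90 × 168 = 151.2, which is not whole, so no tie is possible and the rules coincide.

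**Step 2: average over n = 60 to 400, one recording per subject.**

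| Goal | Strict | As written | Rise (points) | Share of n where the rules differ |
|---|---|---|---|---|
| 0.80 | 3.2% | 3.4% | 0.26 | 18% |
| 0.85 | 3.5% | 3.6% | 0.08 | 5% |
| 0.90 | 4.0% | 4.1% | 0.19 | 8% |
| 0.95 | 5.2% | 5.4% | 0.17 | 4% |

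**Step 3: some subjects give two recordings.** The denominator then varies between resamples and ties become rare. I simulated the subject-level percentile bootstrap with true rate at the goal, independent recordings, 3,000 trials and 2,000 resamples each (Monte Carlo standard error about √(0.05 × 0.95 / 3000) = 0.4 points).

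| Goal | Total recordings | Subjects with two | Strict | As written | Ratio |
|---|---|---|---|---|---|
| 0.90 | 100 | 0 | 3.2% | 6.4% | 2.0 |
| 0.90 | 100 | 1 | 4.7% | 5.8% | 1.2 |
| 0.90 | 100 | 2 | 4.7% | 5.5% | 1.2 |
| 0.90 | 100 | 5 | 5.2% | 5.6% | 1.1 |
| 0.95 | 200 | 2 | 5.1% | 6.4% | 1.3 |
| 0.95 | 200 | 5 | 4.6% | 5.1% | 1.1 |

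Goal × total is whole in every row, yet a handful of two-recording subjects removes most of the effect. With 2,000 resamples the single-recording ratio at goal 0.90, n = 100 is also lower (2.0) than the ideal 2.4.

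**The case against.** The case against giving this weight is strong, and most of it stands.

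- **Size.** A two- to threefold inflation needs goal × n to be whole and essentially every subject in the category to give one recording. That most subjects do so is not enough. The documents allow up to two results per subject in these analyses and give within-subject correlation as the reason for the bootstrap. Nothing in the eligibility criteria keeps a resting sinus rate of 100 or more out of 2c.
- **Reason for the difference.** The secondary hypotheses are blacked out. If a null is written as a rate below the goal, accepting equality simply mirrors it, and Protocol 6.2.2 does describe the 2e target in at-least terms. It therefore cannot be said that the difference has no reason, only that none is readable. This does not alter the arithmetic: under such a null, the same false-success rate is approached as the true rate nears the goal from below.
- **Convention.** With the quantile definition used above, a bound equal to the goal means that less than 2.5% of the bootstrap distribution lies strictly below it (1.15% in the worked example). The rule is prespecified identically in both documents and can be defended on that ground. What it does not explain is a stricter convention for the co-primary endpoints, using the same interval and level.
- **What the edit achieves.** The strict rule already averages 3.2% to 5.2% in Step 2. At goal 0.80 the excess over 2.5% goes from about 0.9 to 0.7 points; at 0.95 from about 2.9 to 2.7. Most of the excess comes from the percentile bootstrap and remains.

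**Conclusion.** The inconsistency is real, appears in both documents, and can act in one direction only, towards success. It is a minor point about secondary endpoints.

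Its size rests on assumed goals and denominators. With one recording per subject and goal × n whole, the false-success rate can rise by about 1.5 to 3 times, although for some such n it does not rise at all. Averaged over n = 60 to 400 the rise is about 0.1 to 0.3 percentage points. With about 2 to 5 two-recording subjects the ratio is about 1.0 to 1.3. With single recordings and goal × n not whole, the effect is zero.

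A reader might infer three stronger things, none of which the documents support:

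- That 2a–2d in this study run at two to three times their nominal error. Whether any tie is possible here cannot be determined from the redacted text.
- That the secondary rule was loosened without justification. The hypotheses that might explain it are redacted.
- That the edit would restore 0.025. It removes only the tie component.

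The co-primary decision is unaffected.

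**What to change.** In SAP 9.7 and Protocol 6.2.2, replace “equals or exceeds” with “exceeds”, matching SAP 9.6 and Protocol 6.2.1. Confirm that the redacted comparison for 2e and 2f is also strict, and align it if not. If the analysis has already been run, state whether any 2a–2d lower bound equalled its goal; if none did, the edit changes no conclusion.

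The cost is one phrase in each document, with no new data, analysis or sample size. The only consequence is that an exact tie would no longer count as success.

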9.8. Additional Analyses

The following additional analyses will be performed.

- 1) Percent correct associated with the Other abnormal rhythm truth category will be estimated as $n77/(N7 - n87)$.
- 2) Percent correct associated with the HR under 50 (HR<50 on simultaneous 12-lead ECG) truth category will be estimated as $n11/(N1-n81)$.
- 3) Percent correct associated with the HR over 150 (HR >150 on simultaneous 12-lead ECG) truth category will be estimated as $n66/(N6-n86)$.
- 4) Percent correct associated with the AF rhythm classification for adjudicated heart rate values between 50-120. The numerator of this percent correct calculation will be the number of test device classifications of AF and test device heart rate between 50-120 with an adjudicated AF rhythm classification and adjudicated heart rate value between 50-120. The denominator will include all classifiable test device results with an adjudicated AF rhythm classification and adjudicated heart rate between 50-120.

Two-sided 95% bootstrap confidence intervals will be constructed during the same bootstrap sampling procedure outlined for the primary and secondary endpoints for these four additional analyses. If the number of samples within any of these categories is ≤ 20 , only summary statistics will be presented.

- 5) The number and percentage of the ECG app Inconclusive and the ECG app Poor Recording trials within each category of ground truth will be reported as well as overall as a percentage of the total number of trials.
- 6) A cross-classification table of the ECG app results with each of the types of Other abnormal rhythm truth categories (outlined in Section 5.2.3.1.2) will be presented.
- 7) Descriptive summary statistics (N, mean, std. dev, min, max) of the paired heart rate differences (bpm) between the ECG app and the 12-Lead ECG will be reported by cohort and overall.

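### Do the bootstrap intervals for the supportive analyses that add Inconclusive, low-rate and high-rate outputs leave out the subjects they are meant to count?

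*SAP*

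**What the plan says.** The tested 2a-2d percentages in SAP 9.7 use only the four SR and AF output rows of Table 9.6 (rows 2 to 5). Their intervals come from resampling subjects who have an adjudicated result in the truth category "and with a classifiable algorithm result will be selected at random with replacement". SAP 9.7 then adds: "Additional secondary endpoint analyses will be performed similarly by including the HR<50, HR>150, and Inconclusive algorithm results in the computations of percent correct". No separate formula or pool is given. Protocol 6.2.2 has the same text.

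The word is spelled out only for the co-primary endpoints in SAP 9.6, where the pool is subjects with an adjudicated AF or SR result "and with a classifiable algorithm result (i.e., SR or AF) will be selected at random with replacement". In Table 9.5 the Inconclusive row also absorbs rates below 50 and above 150; Table 9.6 gives these three outputs separate rows. SAP 9.6 also plans an additional sensitivity and specificity, with bootstrap intervals, "by including the Inconclusive algorithm classification category in the calculation".

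SAP 9.8 covers four further percentages: "Two-sided 95% bootstrap confidence intervals will be constructed during the same bootstrap sampling procedure outlined for the primary and secondary endpoints".

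SAP 8 defines the Classifiable Analysis Set by readable paired results and assigns it to the co-primary endpoints, to 2a-2d and to the additional analyses.

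**The concern.** The additional analyses show how far the headline results depend on setting aside strips to which the app gave no usable rhythm answer. An interval for that purpose must resample the subjects who gave such strips. Read literally, SAP 9.7 widens the percentage but not the pool. A subject whose only strip in a category is labelled Inconclusive would count in the point estimate but could not be drawn for its interval. The interval would then be too high, and in the extreme would repeat the main-analysis interval under another name.

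SAP 9.6 looks like the plainest case, because its gloss expressly limits the pool to SR or AF outputs while the additional sensitivity and specificity add Inconclusive. In SAP 9.8 the correct cells for items 1 to 3 (n77, n11, n66) are themselves Inconclusive, low-rate and above-150 outputs.

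**Working it through.** **Inputs.** The documents give the formulas, the percentile bootstrap and up to two strips per subject (SAP 9.6, 9.7). They state no rate for these outputs and no interval, so there is no plan figure to reproduce. All counts and rates below are assumptions; if no such outputs occur, the gap is zero.

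**1. Extreme case: one in-category strip per subject, classifiable result required on that strip.** Assume 95 of 100 row 2-5 strips correct and k further strips labelled Low HR, HR >150 or Inconclusive. The interval is the 2.5th and 97.5th percentiles of Binomial(N, c/N)/N with c = 95. The restricted pool has N = 100 and gives 90.0-99.0% whatever k is. The matched pool has N = 100 + k:

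| k | Estimate | Matched-pool interval |
|---|---|---|
| 2 | 95/102 = 93.1% | 88.2-98.0% |
| 5 | 95/105 = 90.5% | 84.8-95.2% |
| 10 | 95/110 = 86.4% | 80.0-92.7% |

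At k = 6 the estimate, 95/106 = 89.6%, falls below the restricted pool's lower bound of 90.0%. With 190 of 200 correct, that bound is 92.0% and the crossing comes at k = 7 (190/207 = 91.8%).

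**2. Subject-level reading.** The pool sentence sets two conditions on the subject and does not say that both must be met on one strip. If a classifiable result on the other strip is enough, and 5 of the 10 subjects at k = 10 have one, then N = 105 and the interval is 84.8-95.2%. If all ten have one, the pool is the matched pool and the gap is zero.

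**3. Additional sensitivity (SAP 9.6).** Assume 98% correct when classified, Inconclusive rate q = 0.10, two AF strips per subject and within-subject correlation rho. The share of subjects with both strips Inconclusive is d = q² + rho·q(1−q). The Inconclusive share left in the restricted pool is (q−d)/(1−d). The full-pool estimate is 0.98 × 0.90 = 88.2%.

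| rho | d | Share left | Pool centre | Shift (points) |
|---|---|---|---|---|
| 0 | 0.010 | 0.0909 | 89.1% | 0.9 |
| 0.2 | 0.028 | 0.0741 | 90.7% | 2.5 |
| 0.4 | 0.046 | 0.0566 | 92.5% | 4.3 |

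**4. Tested bounds.** A subject with no strip in rows 2 to 5 adds nothing to the numerator or denominator of 2a-2d. Simulating the 95/100 case with 2, 5 or 10 such subjects added to the pool gives a lower bound of 0.902 against 0.900, so the choice of pool hardly touches the tests.

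**5. Which reading the text supports.**
- In SAP 9.6 the additional estimates and their bootstrap intervals are both to be obtained "by including the Inconclusive algorithm classification category in the calculation". That phrase naturally governs the interval too.
- SAP 8 assigns the additional analyses to a set defined by readable results. Tables 9.5 and 9.6 list Inconclusive and Poor Recording separately, so an Inconclusive strip can be a readable one.
- SAP 9.8 items 1 to 3 concern truth categories (Other, below 50, above 150) that appear in no stated pool. For them the same sampling procedure can only mean the same method, applied to each item's own denominator. Item 4 has a classifiable-only denominator, so the mismatch does not arise.
- For Table 9.6, the meaning rows 2 to 5 follows from the four denominators and the note on bold cells.

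**The case for a change.** The strongest case for a change is that two programmers could follow the same text and produce different intervals. The one-strip case is also realistic for 2a-2d. The categories split at 100 bpm, and the exercise target at age 65 is 0.85 × (220 − 65) = 132 bpm, so many subjects would give one strip at rest in the lower band and one after exercise in the upper band. In a simulation with 150 subjects, 97% correct and one strip each, coverage of the true inclusive percentage under the restricted pool fell to 64%, 18% and 0.4% when 2%, 5% and 10% of outputs were non-classifiable. A matched pool gave about 93-95%. One sentence in the SAP would remove the doubt.

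The silence is real, and so is the arithmetic under that reading. But the coverage figures need the least favourable combination: one strip per category, exclusion decided on that same strip, and a programmer who leaves the pool alone while widening the denominator. The subjects with one strip per band are also those whose other strip would usually keep them in under the subject-level reading. With two in-category strips and independent failures, the same simulation dropped nobody at 2-5%. At 10% with 150 subjects, the intervals were 83.3-91.0% for the full pool and 85.7-92.5% for the restricted one. A restricted-pool interval lying wholly above its own estimate would also be noticed on the output.

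**Conclusion.** No change to the plan is needed. The SAP leaves one word undefined for Table 9.6 and does not spell out the pool for a group of supportive intervals. The natural completion, which is to resample every subject with a strip in that analysis's denominator, agrees with the surrounding text and makes every interval correct.

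Under the literal carry-over the shift would be about 1 to 4 points for the additional sensitivity, given 10% Inconclusive, two strips per subject and correlation between 0 and 0.4. It would be larger only with one strip per category and same-strip exclusion. These rates are assumed, not documented.

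Nothing confirmatory depends on the answer: point estimates come straight from the tables, and performance goals and power do not involve this pool. The dependence on excluded outputs is visible in any case. Table 9.6 shows the three outputs by truth category, and SAP 9.8 item 5 reports Inconclusive and Poor Recording counts and percentages.
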